8.3.11 Therapeutic Phlebotomy

If a subject's Hb exceeds 14.0 g/dL or the rate of rise of Hb raises concern to the investigator, the subject may be phlebotomized based on the investigator's clinical judgment. The method of phlebotomy will be in accordance with the investigative site's guidelines and standard clinical practice.

8.4 **Prior and Concomitant Therapy**

8.4.1 General

All medications (except those routinely administered as part of the dialysis procedure or flushes used for routine catheter maintenance) taken within 30 days prior to Day 1 and through the final study visit should be recorded on the appropriate CRF. In addition, ESA history will be recorded in the CRF.

At each study visit, subjects will be asked whether they have started or discontinued any medication since their previous study visit.

This includes single use or as needed medication use. All medications and treatments, including vitamin supplements, over-the-counter medications, and oral herbal preparations must be recorded on the appropriate CRF.

8.4.2 Erythropoiesis-Stimulating Agents

Subjects are prohibited from taking non-protocol ESAs starting from the screening period and through Week 20, unless the subject permanently discontinues study treatment.

Epoetin alfa rescue therapy is allowed as presented in Section 8.3.10.

8.4.3 RBC Transfusion, Epoetin Alfa Rescue Therapy, Iron Supplementation, and Therapeutic Phlebotomy

Use of epoetin alfa rescue therapy, iron supplementation, and therapeutic phlebotomy within 30 days prior to Day 1 will be recorded.

Receipt of RBC transfusion, epoetin alfa rescue therapy, iron supplementation, and therapeutic phlebotomy during the study will be recorded.

NOTE: RBC transfusion within 4 weeks prior to or during screening is a study exclusion criterion.

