5.2 Secondary Objectives and Endpoints

The secondary objectives of this study are to evaluate the safety and efficacy of vadadustat compared to epoetin alfa in subjects with anemia secondary to DD-CKD who are hyporesponsive to ESAs.

Secondary endpoints:

- Proportion of subjects demonstrating incremental increases in Hb from baseline over time during the treatment period
- Proportion of subjects with Hb values within the target range of 10.0-11.0 g/dL during the treatment period
- Proportion of subjects receiving epoetin alfa rescue
- Proportion of subjects receiving RBC transfusion
- Levels of various biomarkers, including CRP, hepcidin, and vascular endothelial growth factor (VEGF)
- Mean weekly dose of intravenous elemental iron
- Maintenance of iron sufficiency (defined as ferritin ≥100 ng/mL and transferrin saturation [TSAT] ≥20%).
- Resource utilization

Safety endpoints in this study include the following:

- Hb >12.0 g/dL, >13.0 g/dL, or >14.0 g/dL
- Hb increase >1.0 g/dL within any 2-week interval or >2.0 g/dL within any 4-week interval
- AEs and SAEs
- Vital sign measurements and clinical laboratory values

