6.1 Study Design

This is a Phase 2, randomized, open-label study to evaluate vadadustat for the treatment of anemia in subjects with DD-CKD who are hyporesponsive to ESAs. Approximately 50 subjects (n=25 subjects per treatment arm) will be enrolled at approximately 35 investigative sites in the United States.

The study population will consist of subjects with DD-CKD who are ≥ 18 years of age, receiving chronic, maintenance, in-center hemodialysis on an outpatient basis (3 times per week) for end-stage renal disease and for at least 6 months prior to screening, and are hyporesponsive to ESAs

As presented in Figure 2, the study includes a screening period (up to 28 days; Week-4 to Day-4), a study treatment period (from Day 1 to Week 20), and a safety follow-up period (Week 20-24). Therefore, individual eligible subjects will participate in the study for up to 28 weeks. Additional information about each of these study periods is provided below, and clinical and safety assessments will be performed as indicated in Appendix A.

Figure 2 Schematic of the Study Design

Screening Period (Week -4 to Day -4):

The screening period starts at the time the informed consent is signed and will be a maximum of 28 days in duration. The baseline visit on Day 1 will be performed within 28 days of the start of screening and a minimum of 4 days must elapse between the last screening visit and the baseline visit.

Subjects who meet all inclusion and none of the exclusion criteria will be randomly allocated (1:1 ratio) using the interactive web response (IWR) system to participate in either the vadadustat or epoetin alfa treatment arm. Permuted block randomization will be used to assign subjects to treatment.

Study Treatment Period (Baseline [Day 1] to Week 20):

Study drug treatment will aim to maintain Hb level within target range of 10.0 to 11.0 g/dL.

- Vadadustat treatment arm: Subjects who are randomized to the vadadustat treatment arm will discontinue epoetin and will initiate vadadustat dosing at a on Day 1. Additional information on vadadustat dosing adjustments is provided in Section 8.3.5.
- **Epoetin alfa treatment arm**: Subjects who are randomized to the epoetin alfa treatment arm will continue to receive epoetin alfa at the same dose that they were receiving during the screening period. Epoetin alfa dose can be titrated as clinically indicated; and additional information is provided in Section 8.3.4.

Safety Follow-Up Period (Weeks 20 to 24):

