7.2 Inclusion Criteria

Subjects must meet all the following inclusion criteria to be eligible for study participation:

- 1. ≥ 18 years of age
- 2. Receiving chronic maintenance in-center hemodialysis (3 times per week) for end-stage renal disease for at least 6 months prior to screening
- 3. Currently receiving epoetin alfa for anemia
- 4. Two Hb measurements (by central lab analysis) between 8.5 and 10 g/dL during screening
- 5. Administered intravenous supplemental iron per investigative site's protocol to maintain serum ferritin \geq 100 ng/mL and TSAT \geq 20%
- 6. Folate and vitamin B12 measurements \geq lower limit of normal during screening
- 7. Having dialysis adequacy as indicated by k- dialyzer clearance of urea, t- dialysis time, V-volume of distribution of urea (Kt/V) >1.2
- 8. Understands the procedures and requirements of the study, willing and able to comply with all study procedures, and provides written informed consent and authorization for protected health information disclosure

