8.3.9 Iron Supplementation (Information on Allowed Use)

Investigators should prescribe iron supplementation (intravenous, oral, or intradialytic) as needed and maintain ferritin \geq 100 ng/mL and TSAT \geq 20%. The duration, dosage, and frequency of use of supplemental iron should be recorded.

Important: Because of the potential for oral iron to decrease the bioavailability of vadadustat, vadadustat should not be administered concurrently with an oral iron supplements (including

multivitamins containing iron), iron containing phosphate binders, or any medications containing iron. Subjects should be instructed to take any of these medications at least 2 hours before or 2 hours after taking the dose of vadadustat.

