11 DATA ANALYSIS

Data collected throughout the study will be summarized using descriptive statistics and listed in by-subject listings. Continuous variables will be summarized using number of subjects with data, mean, standard deviation, median, minimum, and maximum. For categorical variables, the number and percentage of subjects in each category will be tabulated.

For continuous endpoints (eg, Hb) where change from baseline will be analyzed and multiple pretreatment values are recorded, baseline will be defined as the mean of all qualifying values collected prior to the first dose of study drug. For other continuous endpoints baseline will be defined as the last available value prior to the first dose of study drug.

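### The pre-Day-1 iron use that the trial records is not used for the weekly IV iron endpoint; a baseline-adjusted arm difference would give a modest gain in precision at little cost

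*Combined protocol and SAP*

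**What the plan says.** - **Look-back.** Section 8.4.3: "Use of epoetin alfa rescue therapy, iron supplementation, and therapeutic phlebotomy within 30 days prior to Day 1 will be recorded". Section 8.3.9, on iron prescribed during the study, adds: "The duration, dosage, and frequency of use of supplemental iron should be recorded".
- **Endpoint.** Section 5.2 lists "Mean weekly dose of intravenous elemental iron" among the secondary endpoints, under an objective that compares vadadustat with epoetin alfa. It names no baseline, averaging window, change or covariate.
- **Analysis.** Section 11.6 plans descriptive summaries by treatment group, with 95% confidence intervals where appropriate and no hypothesis tests.
- **Iron practice.** The entry criterion in Section 7.2 reads "Administered intravenous supplemental iron per investigative site's protocol". On study, Section 8.3.9 says "Investigators should prescribe iron supplementation (intravenous, oral, or intradialytic) as needed", with floors for ferritin and TSAT.
- **Design.** Section 6.1: "Approximately 50 subjects (n=25 subjects per treatment arm) will be enrolled at approximately 35 investigative sites in the United States". Section 9.2.5 specifies 1:1 permuted-block randomization and names no stratification factor.
- **Baseline rules.** Section 11 uses the mean of qualifying pre-dose values where change from baseline is analysed and there are several such values. Otherwise: "For other continuous endpoints baseline will be defined as the last available value prior to the first dose of study drug". Section 11.3 plans summaries of pretreatment variables but does not name iron dose.

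**The concern.** Iron dose on study probably depends in part on the iron dose at entry, because both follow local practice and the same patient's needs. At about 50 / 35 = 1.4 subjects per site, with no stated stratification, neither site practice nor entry dose is balanced by design. The plan records entry iron use and then leaves it out of the one endpoint it bears on most directly.

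Because the analysis is descriptive, readers will judge the raw difference between two arms of 25. If the arms happened to start at different iron doses, part of that difference would reflect the starting point. As written, the plan does not commit to showing the imbalance or allowing for it.

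**Working it through.** **What can be reproduced.** The stated sample size is 2 x 25 = 50. Sections 11.1 and 11.6 give no effect size, SD, alpha or power, so there is no design calculation to repeat. Results below are in units of the between-subject SD of weekly IV iron dose, which the documents do not give.

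**Inputs.** n = 25 per arm (Section 6.1). The correlation r between pre-Day-1 and on-treatment weekly dose is not in the documents; 0.3, 0.5 and 0.7 are assumed. Pre-treatment and on-treatment SDs are taken as equal.

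**Step 1: unadjusted difference.** SE = sqrt(2/25) = 0.283 SD. The 95% half-width is t(0.975, 48 df) x 0.283 = 0.57 SD.

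**Step 2: chance imbalance in entry dose.** The entry difference between arms also has SD 0.283. By normal approximation:
- P(imbalance above 0.3 SD either way) = 2[1 - Phi(0.3/0.283)] = 0.29.
- P(imbalance above 0.5 SD either way) = 2[1 - Phi(0.5/0.283)] = 0.077.

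An imbalance of 0.3 SD shifts the expected unadjusted difference in that trial by r x 0.3, that is 0.09, 0.15 or 0.21 SD at r = 0.3, 0.5 or 0.7.

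**Step 3: adjusted analysis and change score.** Adjustment (ANCOVA) multiplies the variance by 1 - r^2. A change score multiplies it by 2(1 - r). The equivalent n per arm is 25/(1 - r^2).

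| r | 1 - r^2 | Adjusted half-width | Interval narrower by, 1 - sqrt(1 - r^2) | Equivalent n per arm | Change-score half-width |
|---|---|---|---|---|---|
| 0.3 | 0.91 | 0.54 SD | 5% | 27.5 | 0.67 SD |
| 0.5 | 0.75 | 0.49 SD | 13% | 33.3 | 0.57 SD |
| 0.7 | 0.51 | 0.41 SD | 29% | 49.0 | 0.44 SD |

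The change score is worse than the unadjusted 0.57 SD at r = 0.3, gains nothing at r = 0.5, and is wider than the adjusted analysis throughout.

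**Step 4: simulation check for bias.** Each scenario used 8,000 trials with 50 subjects over 35 sites, unstratified permuted blocks of 4 (block size assumed), and a true effect of -0.30 SD. Site was given an assumed 20%, 30% or 50% of the variance, paired with r = 0.3, 0.5 or 0.7. The unadjusted difference averaged -0.30 SD every time, so site practice added no systematic bias. The SE was 0.28, 0.29 and 0.28 unadjusted; 0.27, 0.25 and 0.21 adjusted; and 0.34, 0.29 and 0.22 for the change score.

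**The case against.** The strongest reply is that a randomized, concurrent epoetin alfa arm makes a baseline unnecessary. The on-treatment difference already estimates iron sparing against epoetin alfa, and its interval already allows for chance imbalance on average. That stands. A reader might infer that the endpoint cannot show iron sparing, or that site practice biases it; 1:1 randomization and the simulation support neither. Section 4.4 also assigns assessment of the iron-sparing effect to the Phase 3 studies, so this trial is not presented as the test of it.

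A reader might also infer that Section 11 prescribes the wrong baseline for iron, since the last value before dosing would be a single administration. The documents do not establish this. No change from baseline is planned for iron, and if one were, the mean-of-values rule would be the first candidate. Neither rule spells out a weekly dose, but that is a definition to add.

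Three practical objections hold in part:
- Section 8.4.3 promises only use in the look-back, and Section 8.4.1 exempts medications given routinely with dialysis from general recording. Dose capture before Day 1 therefore has to be confirmed.
- Section 7.4.2 allows rescreening after replacement therapy for low ferritin or TSAT, so some look-backs may contain repletion iron. A raw change could then show a fall unrelated to study drug. An adjusted difference stays valid, because the look-back precedes treatment, but r may be lower.
- Section 6.2 says that most of the study runs at one dialysis provider's centers, so practice may vary less than 35 sites suggest. The documents give no dose distribution.

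Finally, Amendment 1 deliberately made the analysis descriptive, and Section 11.6 specifies no model for any endpoint. That limits the weight of the point. An estimate with an interval is nonetheless compatible with a plan that has no tests.

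**Conclusion.** The point holds as a minor improvement in precision. Entry iron use is recorded and left out of a comparative endpoint. What is lost is precision, together with protection against an imbalance that would exceed 0.3 SD in about 29% of trials this size. The gain runs from slight (half-width 0.57 to 0.54 SD at r = 0.3) to useful (0.41 SD at r = 0.7). It rests on the assumed r, which roughly four weeks of possibly episodic dosing may keep low, and on normal-theory approximations for a dose that may be skewed with zeros. The unadjusted difference remains a valid estimate, and no conclusion about the primary endpoint is affected.

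**What to change.** In Sections 5.2 and 11.6:

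1. Confirm that the case report form captures the dates and elemental doses of IV iron in the 30 days before Day 1, as well as whether iron was used.
2. Define baseline as the mean weekly IV elemental iron dose over those 30 days (total mg / 30 x 7), and state the on-treatment averaging window.
3. Show baseline dose by arm.
4. Beside the planned unadjusted summaries, report the vadadustat-minus-epoetin difference in on-treatment weekly dose adjusted for baseline, with a 95% interval, a rank-based check for skew and zeros, and no formal test.
5. Do not use a raw change score for the arm comparison.

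The cost is a few lines of wording, one extra descriptive model and its check, and possibly a change to the case report form if look-back doses are not captured. No visits or tests are added.

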8.4.4 Dialysis Treatment and Renal Replacement Therapy

Information on dialysis treatment, including dialysis vascular access type, dialysis adequacy, and history of and changes in renal replacement therapies, will be recorded.

8.4.5 Investigational Medications

Study subjects should not have received any investigational medication or participated in an investigational study within 30 days or 5 half-lives of the investigational medication (whichever is longer), prior to screening. In addition, subjects should not have participated in a study with another HIF-PH inhibitor other than vadadustat.

Subjects should not take another investigational medication while participating in this study.

9 STUDY PROCEDURES AND SCHEDULE OF ACTIVITIES

9.1 Schedule of Visits

If possible, study visits should be scheduled on the day of the first hemodialysis session of the week to allow for the turnaround time for central lab Hb values (and dose adjustment as needed) before the end of the workweek.

As presented in Appendix A, this study includes the following visits:

- Eligibility screening period (from Day -28 to Day -4; screening must be performed within 4 weeks prior to dosing on Day 1 and the last screening visit must be completed at least 4 days before dosing starts on Day 1 to allow for laboratory test results to be available prior to initiation of study drug)
 - Screening visit 1
 - Screening visit 2
- Study treatment period (from Day 1 to Week 20 visit)
 - Baseline visit (Day 1)
 - $\circ \quad \text{Week 2 visit} \pm 3 \text{ days}$
 - Week 4 visit \pm 3 days
 - $\circ \quad Week \ 6 \ visit \pm 3 \ days$
 - $\circ \quad Week \ 8 \ visit \pm 3 \ days$
 - \circ Week 10 visit \pm 3 days
 - Week 12 visit \pm 3 days
 - $\circ \quad Week \ 14 \ visit \pm 3 \ days$
 - Week 16 visit \pm 3 days
 - $\circ \quad \text{Week 18 visit} \pm 3 \text{ days}$
 - \circ Week 20 visit \pm 3 days (end-of-treatment visit)
- Safety follow-up period
 - $\circ \quad Week \ 24 \ visit \pm 5 \ days$

9.2 Administrative Procedures

9.2.1 Screening Documentation

Investigators will maintain documentation of all study candidates evaluated and reasons that subjects who were considered for the study did not qualify.

Investigators must account for all subjects who sign informed consent and will maintain a log of subjects screened and indicate who was randomized or excluded. If the subject is found to be ineligible for randomization, the reason(s) for ineligibility and not proceeding to screening or study enrollment, must be documented by the investigator.

Screening numbers assigned to subjects who fail screening will not be re-used.

The investigator will maintain a log of subjects and indicate who was enrolled or excluded and the reason for exclusion (see Section 9.2).

9.2.2 Informed Consent

Informed consent must be obtained and legally signed prior to a subject's entry into the study and before any protocol-directed procedures (including screening tests) are performed (see Section 15.3). After providing informed consent and receiving a unique subject identification number, subjects will undergo various screening activities. Additionally, subjects will be asked to provide separate written informed consent for the collection and storage of a blood sample for future genetic analyses.

9.2.3 Review of Inclusion and Exclusion Criteria

A subject must meet all inclusion criteria listed in Section 7.2 to be eligible for study participation.

A subject who meets any of the exclusion criteria listed in Section 7.3 will not qualify for study participation.

9.2.4 Acceptable Methods of Contraception

In nonclinical animal embryo-fetal development and fertility studies, there was no evidence of teratogenicity, no skeletal or visceral malformations, and no changes in male or female reproductive and fertility indices, or in sperm parameters. In rats, decreased fetal body weight and reduced skeletal ossification were noted at the highest dose tested of 160 mg/kg/day. Peri-postnatal development studies of vadadustat in the rat are ongoing, and there are no data on the transmission of vadadustat in breast milk or the effect of vadadustat on infants.

The potential risk of vadadustat on the developing fetus is limited based on available study results. However, this protocol requires that all subjects must agree to use acceptable methods of contraception throughout the study and for 30 days after the last dose of study drug. In addition, men must not donate sperm during the study and for at least 90 days after the last dose of study drug.

Acceptable methods of contraception are defined as follows:

- Female subjects must be surgically sterile or postmenopausal (no menses for at least 1 year)
- Female subjects of childbearing potential (ie, are not surgically sterile or postmenopausal) must have negative pregnancy test results (see Section 9.3.2 for information on pregnancy tests)
- Female subjects of childbearing potential (ie, are not surgically sterile or postmenopausal) and male subjects who are not vasectomized must practice at least one of the following acceptable methods of contraception:
 - Total abstinence from sexual intercourse, with a minimum of one complete menstrual cycle prior to screening visit, throughout the study, and for 30 days after the last dose of study drug
 - A vasectomized partner
 - Hormonal contraceptives (oral, parenteral, or transdermal) for at least 3 months prior to study drug administration, throughout the study, and for 30 days after the last dose of study drug
 - Intrauterine contraceptive device starting at the screening visit, throughout the study, and for 30 days after the last dose of study drug

 Double-barrier method (such as male condom, female condom, diaphragm, sponge, or cervical cap together with spermicidal foam, gel, film, or suppository) starting at the screening visit, throughout the study, and for 30 days after the last dose of study drug.

9.2.5 Randomization

Subjects who meet all inclusion and none of the exclusion criteria will be randomly allocated (1:1 ratio) using the IWR system to participate in either the vadadustat or epoetin alfa treatment arm. Permuted block randomization will be used to assign subjects to treatment.

9.3 Study Procedures and Evaluations

9.3.1 Clinical and Safety Assessments

The following clinical evaluations will be conducted during the study. Detailed information regarding the timing of the assessments is presented in Section 9.4 and summarized in Appendix A. Clinical evaluations should be completed prior to dialysis on the day of the visit, if applicable.

- Demographics and medical history: Relevant medical history (with emphasis on previous medical conditions that may lead to exclusion) and significant ongoing medical conditions or diseases should be documented.
- Physical examination: Physical examination, including height measurement. After the screening period, an abbreviated, symptom-directed physical examination may be performed based on investigator's clinical judgment.
- Dry weight, dialysis adequacy, and dialysis treatment review: Dry weight will be recorded. Dialysis adequacy (measured as Kt/V), as available from local collection, will be recorded. Dialysis treatment will be reviewed including frequency of dialysis and vascular access type (eg, arteriovenous fistula, arteriovenous graft, and venous catheter).
- Vital signs: Vital signs will include blood pressure, heart rate, respiratory rate, and body temperature. Blood pressure and heart rate will be collected in the seated position after 5 minutes of rest. Vital signs should be collected prior to blood draws, when possible.
- 12-lead electrocardiography (ECG): A standard 12-lead ECG should be obtained after the subject has been resting comfortably in a supine position for approximately 10 minutes. ECGs should be taken prior to blood draws when possible. The subject should consume no more than a light meal or snack during the 1-hour period prior to the ECG. With the subject in a supine position obtain the 12-lead tracing. Each 12-lead ECG must be recorded with a paper speed of 25 mm/sec and printed as a paper copy. The investigator (or a qualified observer at the investigational site) will interpret the ECG and record the results including the following parameters: Heart rate, PR interval, QT interval, QRS interval, and QTc (corrected). All abnormal rhythms will be reviewed by the study physician for the presence of rhythms of potential clinical concern. A printed record of the tracing(s) of the clinically significant rhythm(s) will be made and retained with other source documents.
- Adverse event review: Beginning with the first dose of study medication and through the follow-up visit, the investigator and study personnel will review each subject's laboratory and clinical evaluation findings and query the subject directly regarding AEs. Additional

information is provided in Section 10 and follow-up of unresolved AEs, SAEs, and non-serious events is described in Section 10.3.6.

• Concomitant medication review: All medications taken within 30 days prior to the start of study medication and through the final study visit should be recorded on the appropriate CRF. See Section 8.4 for additional information.

